Subjects will be instructed on the use of a vaporizer at the visit prior to Week 1. The manufacturer's instructional brochure (Appendix 6) will be reviewed. In order to ensure consistency of dosing throughout the study, they will also be instructed on the use of the Foltin puff procedure at the visit prior to Week 1 (Appendix 7). A copy of both of these documents will be provided for review at home.

On completion of eight weeks of treatment or at the time of withdrawal from the study, patients will completely taper their cannabis over a period of one to two weeks to avoid withdrawal symptoms. Cannabis withdrawal symptoms will be measured via a phone call after Taper weeks 1 and 2 (Appendix 8). Questions (Appendix 26) will be added to access subject's beliefs of what they received (e.g., THC or placebo) after the first week and again after the eighth week. This will enable us to assess the effectiveness of blinding and thus report on the assay sensitivity of the study. The optimal

timing and frequency of blinding assessments has not been established. Thus, we will use a strategy to collect blinding data two times from participants: shortly after randomization and at the end of the trial. This will permit a comparison of blinding at the two stages.

If a subject does not participate in the driving simulation or the microbiome substudy, we will test their oral fluid for the presence of THC using the Draeger 5000. This will be done to exclude participants who use their own cannabis seeking pain relief because they were given placebo.

An online questionnaire will be deployed (Appendix 27). Potential participants will complete this using HIPAA compliant software, the Platinum Edition of Survey Monkey. Please see <https://www.surveymonkey.com/pricing/details/> for verification of the HIPAA compliance of this survey.

Outcome Measures:

DAILY TESTING IN SUBJECT'S RESIDENCE USING PAPER DIARY

Medication intake: The timing and number of puffs of vaporized cannabis or placebo THC), oral medication (dronabinol or placebo), and breakthrough pain medication will be chronicled. (5 minutes)

REPEATED TESTING AT STUDY VISITS

Center for Medicinal Cannabis Research Forms

- Neurobehavioral Medical Screen: The clinician will fill this out to record any events that may have occurred between visits to confound results from the Neuropsychological testing such as an any trauma to the head or any open head wounds.

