- Behavior Notes Instrument: The clinician will fill this out during Neuropsychological testing to note confound variables associated with participant during the appointment.
- Adverse Events Form: A form to be filled out by the clinician that records any adverse events that have occurred since the last appointment due to study medication.

NIH Task Force on CLBP Impact Score

The impact score is a novel combination of 3 constructs; pain intensity, interference, and function. It is assembled in the Repeated Measures Recommended Minimal Dataset (Appendix 9).⁹

Pain Relief

Neuropathic Pain Scale: This instrument has an ordinal scoring of one to ten for several characteristics of neuropathic pain.^{10, 11} Specifically, the responses measure pain characteristics such as intensity, sharpness ("like a knife"), burning ("on fire"), aching ("like a bruise"), cold ("freezing"), sensitivity ("like raw skin"), itching ("like poison oak"), unpleasantness ("intolerable"), and the amount of deep versus superficial pain. (5 minutes)

Mood Evaluation

Profile of Mood States (POMS): The POMS measures six identifiable mood or affective states: 1) Tension-Anxiety 2) Vigor-Activity 3) Depression-Dejection 4) Fatigue-Inertia 5) Anger-Hostility 6) Confusion-Bewilderment. The POMS can be re-administered on a weekly basis, which is long enough to detect the respondent's mood responses to his or her current life situation, but short enough to assess acute treatment effects. Sixty five items rated from 0 to 4 and scored in terms of total mood disturbance.¹² (10 minutes)

Beck Depression Inventory-II (BDI-II): The BDI-II is a twenty-one item depression scale in which participants can rate depressive symptoms and attitudes from 0 to 3 in terms of intensity.¹³ We will measure clinical depression using the BDI-II and will include this measurement in analyses to provide an adjusted view of analgesia and side-effects. (3 minutes)

Neuropsychological Testing

WAIS-III Digit Symbol test: a test of concentration, psychomotor speed, and graphomotor abilities. This pen and paper test involves having subjects substitute a series of symbols with numbers as quickly and accurately as possible during a 120 second period. The results are expressed as the number of correct substitutions.¹⁴ (10 minutes).

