Cannabis Withdrawal Scale: The Cannabis Withdrawal Scale can be used as a diagnostic instrument in clinical and research settings where monitoring of withdrawal symptoms is required.²² This will be performed after the 2-week tapering period has concluded. (10 minutes) If there was a previous adverse event or events (AE(s)), the Cannabis Solicited Adverse Events instrument will again be administered to ensure that the AE(s) have resolved. Participants will continue to be followed until there is resolution of the AE(s).

ARM #2. Driving Simulation:

Subjects with drivers’ licenses will be scheduled for two experimental visits; one before they begin the randomized controlled trial, and a second visit after finishing their 8th week treatment. The initial visit will involve a 20-minute session to garner baseline values for driving skills. This visit will coincide temporally with the first session for the randomized controlled trial prior to Week 1 (Appendix 12).

At the time of the second driving simulation visit, subjects will be assigned the same medication that they have been using during the randomized controlled trial. Using a Volcano Vaporizer, subjects will inhale the average number of puffs they had consumed per session throughout the four previous weeks of the randomized controlled trial. They will use the Vaporizer before Hour 2 and again before Hour 6 (Table 3). They will also take the same oral medication that was provided during the randomized controlled trial. In addition to examining the effects on driving simulation, acute effects of study medications on spontaneous pain and vital signs will be determined (Appendix 13). We will administer the simulator sickness assessment during the first 2 hours of the appointment to ensure that the participant is physically able to perform the driving simulation tasks.

At the beginning of driving simulation appointments, participants will be given a urine toxicology and a breathalyzer test to test for any illicit substances that is not prescribed by a physician. Should the participant screen positive for an illicit substance, they will either be asked to reschedule or be discontinued from the study at the Principal Investigator's discretion. If this happens, participants will be compensated \$10 for arriving to the scheduled appointment.

During the Driving Simulation study visit, the participants will be given paper and pencil forms that measure the following:

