15. RISK MANAGEMENT PROCEDURES AND ADEQUACY OF RESOURCES

At every study visit, stopping criteria will include:

Pulse: an irregular pulse or pulse rate > 110 beats per minute

Blood Pressure: systolic blood pressure > 180 mmHg or diastolic > 110 mmHg

Respirations: respiratory rate > 20 breaths per minute

Pulse: an irregular pulse or pulse rate greater than 110 beats per minute will result in cessation of participation and, if deemed advisable by a study clinician, transfer to the emergency department (across the street from our research center).

Blood Pressure: If the systolic blood pressure is ≥ 160 to < 180 mmHg or the diastolic is ≥ 100 to < 110 mmHg, a study clinician will conduct an evaluation to see if the participant has symptoms that would mandate discontinuation. Examples would include severe headache, confusion, chest pain, dyspnea, irregular heartbeat, and/or palpitations. Final determination regarding possible discontinuation will be made by a study investigator. If discontinued from the study, the participant will be asked to have their blood pressure evaluated by their primary care physician as soon as possible. If the systolic blood pressure is > 180 mmHg or the diastolic is > 110 mmHg, the participant will be discontinued from the study and either be transferred to the emergency department or be asked to visit their primary care physician as soon as possible. The end organ response to the blood pressure will guide the clinician's decision (e.g., the development of angina pectoris or hemiplegia will mandate transfer to the emergency department).

Respirations: shortness of breath will result in potential cessation of participation and possible transfer to the emergency department following evaluation by a study clinician, who will consult with the study investigator.

A locally developed self-report instrument, the Cannabis Solicited Adverse Events (Appendix 29) will be administered to assess distress from psychological effects of cannabis. This will be performed on a prn basis by the trained staff and routinely at the end of the acute

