administration session. The items on this instrument ask participants about experiencing anxiety, paranoia, and hallucinations. Excess intoxication will also be assessed using this instrument which asks participants about their having dizziness, drowsiness, confusion, emotional changes, and/or cognitive changes. Positive responses to these items, if Grade 2, 3 or 4 (see below for definitions), will result in notification of a study clinician who will speak with the participant to see if discontinuation of participation in the study would be in her or his best interest.

Using the Cannabis Solicited Adverse Events instrument mentioned above, an Adverse Events Form (Appendix 30) will be completed. Adverse events will be characterized as 1 = Mild, 2 = Moderate, 3 = Severe, and 4 = Life Threatening using the following definitions (consistent with those used by the National Cancer Institute):

GRADE 1 MILD	GRADE 2 MODERATE	GRADE 3 SEVERE	GRADE 4 POTENTIALLY LIFE-THREATENING
Mild symptoms causing no or minimal interference with usual social & functional activities with intervention not indicated	Moderate symptoms causing greater than minimal interference with usual social & functional activities with intervention indicated	Severe symptoms causing inability to perform usual social & functional activities with intervention or hospitalization indicated	Potentially life-threatening symptoms causing inability to perform basic self-care functions with intervention indicated to prevent permanent impairment, persistent disability, or death

Inasmuch as the scoring of Grades 2, 3, and 4 mention that an intervention is indicated, AEs with Grades 2 or 3 will be brought to the attention of a study clinician so that s/he may interact with the participant to determine if discontinuation of study participation is warranted. This will be done in consultation with an investigator. Grade 4 AEs will be managed by reports tendered to the FDA and the IRB within the required time limits specified by each organization. There will also be a determination of whether the AE is related, possibly related or not related to the study by the investigator for Grades 1 to 4.

Furthermore, the participant will be followed by the research team to insure that the AE(s) resolve. This might include recommending that the participant see their primary care physician (e.g., for a change in blood pressure medication).

Risks will also be mitigated using the following measures:

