3.1 Adverse events

The number (%) of subjects with adverse events will be tabulated and summarized overall and by treatment arm, with the grade of the adverse event (1-4) included. The study week and reasons for adverse events will be included. Using the Kruskal-Wallis rank sum test, the number of adverse events per individual and maximal grade for each individual were compared among the three treatment arms. The proportion of participants with severe adverse events (leading to permanent treatment determination) will be compared between treatment arms with Fisher's exact test using the strategy of the comparison described in 2.2.

4. Endpoints

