4.1.1 Primary analysis

The primary analysis will be the comparison of self-reported pain intensity between arm A and arm B. An intent-to-treat analysis will be performed on data from participants who complete baseline. Data transformation (e.g., log10, square root) may be performed to improve distribution normality as appropriate. Response profiles analysis will be performed if the trend of pain intensity over time is not linear. We will compare different covariance pattern models (e.g., unstructured, compound symmetry) based on AIC and identify a covariance model with the best fit to our data. This is a randomized controlled trial so that we can remove main group effect with assumptions about equal mean responses (i.e., pain scores) at baseline for the three treatment arms. Weekly or biweekly average of pain intensity from the daily diary will be calculated as a primary outcome. Time will be treated as a factor with 6 levels (i.e., baseline, weeks 1, 3, 5, 7, 8), and the mean response profiles will be compared between the arms. The treatment effect over time will be assessed by the significance of the treatment arm x time interaction using Wald test. Also, average change at the treatment period (weeks 5-8) from baseline will be compared between the groups. (Aim 1)

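### In the taper, solicited AE assessment is conditional on a previous AE and SAP 3.1 sets no AE window, so first taper events are not systematically collected and ascertainment can differ by arm

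*Protocol*

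**What the plan says.** **Exposure.** SAP section 1 names tapering (weeks 9-10) as one of three study periods. Protocol section 9, Table 1, still allows up to 21 tablets a week and 9 puffs a day in Taper Week 1, and 7 tablets and 4 puffs in Taper Week 2.

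**Visits.** SAP 4.1.1 lists the time points: "Time will be treated as a factor with 6 levels (i.e., baseline, weeks 1, 3, 5, 7, 8". None falls in the taper. At study visits the clinician completes a form that "records any adverse events that have occurred since the last appointment due to study medication" (Protocol section 9).

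**Taper contact.** Protocol section 9 says "Cannabis withdrawal symptoms will be measured via a phone call after Taper weeks 1 and 2", with no condition on AE history. Further on, under telephone testing after the taper, the same section adds: "If there was a previous adverse event or events (AE(s)), the Cannabis Solicited Adverse Events instrument will again be administered". The stated purpose is "to ensure that the AE(s) have resolved".

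**Other uses of the instrument.** Protocol section 15 says of it: "This will be performed on a prn basis by the trained staff and routinely at the end of the acute" administration session. It feeds the AE record: "Using the Cannabis Solicited Adverse Events instrument mentioned above, an Adverse Events Form (Appendix 30) will be completed".

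**Analysis.** SAP 3.1 states: "The number (%) of subjects with adverse events will be tabulated and summarized overall and by treatment arm". It tests the AE count per participant and each participant's highest grade across the three arms by Kruskal-Wallis, and severe events that end treatment by Fisher's exact test. It reports study week but does not say which weeks are analysed.

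**The concern.** Whether someone is asked the AE items for weeks 9-10 depends on whether that person already had an AE. That is a post-randomisation outcome which treatment can affect: Protocol section 14 lists several effects of the study drugs as likely. Two things are at stake. Safety information from a period on study drug may be incomplete for people with no AE in weeks 1-8. And if taper events are pooled into SAP 3.1, a larger share of one arm than of another may have been asked about them, so the comparison of counts and grades would partly reflect who was asked.

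**Working it through.** The documents give no AE rate and no calculated figure on this point, so there is nothing to reproduce. The check is a list of routes, then an illustration on assumed rates.

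**Routes by which a taper event could reach SAP 3.1**

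| Route | Who | Covers a new AE in weeks 9-10? |
|---|---|---|
| Clinician's AE form at visits (Protocol 9) | Everyone | No visit after week 8 |
| Solicited instrument at the post-taper call (Protocol 9) | Only those with a previous AE | Meant to check resolution; re-asking the items could reveal new events |
| Same instrument as needed (Protocol 15) | Whoever prompts it | Possible, not scheduled |
| Same instrument after the acute session, taken to be the driving visit (Protocol 15) | Licensed participants who take part | Timed at completion of 8 weeks' treatment, so it does not look back over the taper |
| Withdrawal calls (Protocol 9, SAP 4.2.2) | Everyone | Ask the withdrawal scale; analysed separately as intensity and impact |
| Weekly calls between visits (Protocol 9) | Everyone | Described as compliance and questions; AEs not named |

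Only the second row is a specified AE assessment of the taper, and it is conditional.

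**Illustration (all rates assumed).** Let p be the risk of at least one AE before the taper, t the risk of an AE in the taper (independent of earlier AEs), and s the share of first taper events that surface by other routes. Taper events in people with an earlier AE are taken as fully captured.

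- True any-AE = 1 − (1 − p)(1 − t)
- Recorded any-AE = p + (1 − p)·t·s
- Recorded taper AE = p·t + (1 − p)·t·s
- Missed = (1 − p)·t·(1 − s)

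*Equal taper risk: p = 70% (active) and 40% (placebo), t = 15% in both, s = 0.*
- True: 1 − 0.30 × 0.85 = 74.5%; 1 − 0.60 × 0.85 = 49.0%; gap 25.5 points.
- Recorded: 70% and 40%; gap 30 points.
- Taper events, truly 15 per 100 in each arm, are recorded as 0.70 × 15 = 10.5 and 0.40 × 15 = 6.0.
- Among the 33 completers per arm that SAP 2.2 expects, missed first events are 33 × 0.30 × 0.15 ≈ 1.5 people and 33 × 0.60 × 0.15 ≈ 3.0 people.

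*Unequal taper risk: same p, t = 30% (active) and 10% (placebo), s = 0.*
- True: 1 − 0.30 × 0.70 = 79%; 1 − 0.60 × 0.90 = 46%; gap 33 points.
- Recorded: 70% and 40%; gap 30 points.

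The direction has reversed. At these values of p the missed shares are 0.30·t(active) and 0.60·t(placebo), so the recorded gap is too small whenever the active taper risk is more than twice the placebo risk.

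*Range with equal t.* The excess in the recorded gap is [p(active) − p(placebo)]·t·(1 − s). For p = 30% against 50% or 70%, and t = 10% to 30%:
- s = 0: from 0.20 × 0.10 = 2 points to 0.40 × 0.30 = 12 points.
- s = 0.5: from 1 to 6 points.
- p equal in both arms: 0 points, although first taper events are still under-counted.

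**The case against.** The strongest defence is that the sentence describes follow-up of known events and was never meant as taper surveillance. Everyone is telephoned in the taper, staff may use the instrument whenever something prompts it, and an AE form is completed from it. The call guides are in Appendices 5 and 8, which are not available here and might ask about AEs. Withdrawal, the obvious new risk in this period, is measured in all participants. Those at issue have already gone through weeks 1-8, with maxima of up to 42 tablets a week and 18 puffs a day, without an AE, so few first events may be left to find. The any-AE proportion is only tabulated; the tests are on counts, highest grade and severe events. The pairwise order in SAP 2.2 puts the two active arms first, and their earlier AE rates may be similar.

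Much of this stands. A reader might infer that a first taper event cannot be counted at all. The documents do not support that, because as-needed use and the withdrawal calls are real routes. Nor does any text say that new items reported at the resolution check become new AE counts, although section 15 makes it possible. What the defence does not supply is a scheduled AE question for people without a previous AE, or a statement in SAP 3.1 that weeks 9-10 are left out.

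**Conclusion.** The point holds as a gap in systematic collection together with an undefined analysis window. Both are plain in the text, subject to one limit: Figure 1 is not shown, so the visit timing rests on SAP 4.1.1.

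An effect on the between-arm comparison is conditional. It requires that taper events enter SAP 3.1 and that the share of first taper events missed differs by arm. A reader might infer that the rule always exaggerates the difference between active treatment and placebo. That follows only if taper AE risk is equal across arms and the active arm had more earlier AEs; the 30%/10% example gives the opposite. The documents give no rates, so neither size nor direction can be stated. Under the assumptions shown, the distortion in the any-AE gap runs from none to 12 points. The primary endpoint is unaffected. This is an inexpensive improvement to safety capture and does not threaten the trial's main conclusions.

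**What to change.** 1. **Protocol section 9, telephone testing after the taper:** administer the Cannabis Solicited Adverse Events instrument to every participant at the taper calls already scheduled, whatever their AE history. Keep the resolution check for earlier events.
2. **SAP 3.1:** state the AE window. Make the between-arm comparison on events through the week-8 visit and tabulate weeks 9-10 separately by arm. Study week is already to be reported, so the split needs no new data. Say how events are classed for someone who withdraws early and tapers before week 8.
3. **Call timing:** reconcile the three descriptions, namely after Taper weeks 1 and 2 (Protocol section 9, taper text), after the two-week taper (Protocol section 9, telephone testing) and weeks 8 and 10 (SAP 4.2.2).

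The second change alone would protect the comparison but leave the gap in taper safety data. The first closes that gap: with everyone asked and answering fully, the recorded any-AE proportion equals 1 − (1 − p)(1 − t) in each arm. The cost is a few minutes per call and a few lines of text.

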Both of the above studies were 6-hour human laboratory experiments. The present study is designed to evaluate whether or not the medium dose of cannabis (3.5%) can maintain an analgesic response over an eight-week period. In addition, a direct comparison of this vaporized preparation will be made with dronabinol and placebo. The medium dose of cannabis (3.5%) has been selected as it was utilized in a human experimental laboratory experiment that compared inhaled Δ9-THC and dronabinol.⁶ Using the cold-pressor test, participants immersed their hand in cold water (4 degrees C), and the time to report pain (pain sensitivity) and withdraw the hand from the water (pain tolerance) was recorded. Compared with placebo, marijuana and dronabinol decreased pain sensitivity, increased pain tolerance, and decreased subjective ratings of pain intensity. The magnitude of peak change in pain sensitivity and tolerance did not differ between marijuana and dronabinol, although dronabinol produced analgesia that was of a longer duration. Marijuana and dronabinol also increased abuse-related subjective ratings relative to placebo; these ratings were greater with marijuana. These data indicate that under controlled conditions, marijuana and dronabinol decreased pain, with dronabinol producing longer-lasting decreases in pain sensitivity and lower ratings of abuse-related subjective effects than marijuana.

A direct comparison of cannabis and dronabinol has not been performed in a clinical population. The present study will fill this void by performing a randomized, double-blind placebo controlled 8-week trial comparing the effectiveness of oral versus vaporized cannabis in patients with chronic low back pain. In addition to studying efficacy, we will also perform a driving simulation study to determine the real-world impact of cannabinoid treatments.

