- Presence of another painful condition of greater severity than the back pain condition which is being studied.
- History of traumatic brain injury.
- Clinically significant or unstable medical condition. Individuals with significant cardiovascular, hepatic or renal disease, uncontrolled hypertension, and chronic pulmonary disease (eg, asthma, COPD), will be excluded. With respect to cardiovascular and pulmonary status, a clinician will screen participants with a tool developed for detection of congestive heart failure, coronary artery disease, obstructive and/or restrictive lung disease (Appendix 28 Cardiopulmonary Screen). Hepatic and renal disease will be evaluated with liver and renal function laboratory tests. If warranted clinically, subjects will undergo further evaluation (urinalysis, electrocardiogram, and/or chest X-ray).
- A positive result on toxicity screening will exclude individuals from participation. A urine drug test that screens for 5 categories of drugs: marijuana ($\Delta 9$ -THC), cocaine, amphetamines/methamphetamines, opiates, benzodiazepines and phencyclidine (PCP) will be employed. A positive result for opioids and/or THC will not be exclusionary if the patient is receiving a prescription for an opioid and/or THC.
- Allergy to sesame oil, lactose, or gelatin
- Vascular disease, especially Raynauld's syndrome, systolic blood pressure > 170 mm, diastolic blood pressure > 100 mm
- Recent injuries to the upper extremity
- Cognitive impairment, such as Dementia or Alzheimer's Disease
- Substance Abuse History: individuals with current substance use disorders⁵⁵ as assessed using the Drug Abuse Screening Test (DAST-10) (a score greater than or equal to 3) and the Alcohol Use Disorders Identification Test (AUDIT) (a score greater than or equal to 8 or a score greater than or equal to 7 if over 65 years old) (Appendix 31).
- Pregnancy as ascertained by a mandatory commercial pregnancy test
- Women who are lactating

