- **Economic harm:** Eligibility for insurance, political campaigns, and standing in the community are problems may result from loss of confidentiality. Vaporizing marijuana may hinder application for future employment, if drug screening is a condition of employment. It is likely that detectable traces of marijuana will remain in the subject's hair or blood for a minimum of six weeks after vaporizing. If applicable, a letter will be written to the subject's employer explaining their participation in this research study and the dates of participation. Confidential information regarding your history, DNA information (genetic risk for certain diseases), substance use or health diagnosis may become known outside of the research setting.
- **Reproductive risks:** The procedures in this research are known to hurt a pregnancy or fetus in the following ways: poor educational attainment. A participant should not become pregnant or father a baby while on this study because the drugs in this study can affect an unborn baby. Women should not breastfeed a baby while on this study. Subjects will need to use birth control while on this study. Acceptable methods of birth control are: oral contraceptive pills, diaphragm and condom with spermicide, progestin implant, intrauterine contraceptive device.
- **Unknown Risks:** The experimental treatments may have side effects that no one knows about yet. The researchers will let subjects know if they learn anything that might make you change your mind about participating in the study.

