Dronabinol and Vaporized Cannabis in Chronic Low Back Pain

Statistical analysis plan

Principal investigators:

**[name].
[name]. (retired)**

Protocol Statisticians:

**[name].
[name].**

April 24, 2020

1. Summary of Study Design

This study is a prospective, randomized, placebo controlled, double blind, phase 2/3 clinical trial of dronabinol and vaporized cannabis for the treatment of chronic low back pain. A total of 120 (n = 120) subjects with chronic low back pain, aged between 19-70 years will be randomized in a ratio of 1:1:1 to the three treatment arms (40 participants per arm): 1) vaporized 3.7% Δ9-THC /5.6% cannabidiol plus placebo oral pills, 2) oral Δ9-THC (dronabinol) plus vaporized placebo, and 3) double placebo. The three arms are shortly called 1) vaporized cannabis; 2) dronabinol; 3) placebo. After randomization, each patient will receive study medication at home for 8 weeks after which they will be tapered off of investigational treatments over two weeks. The three study periods include: i) Titration (weeks 0-4); ii) Treatment (weeks 5-8); iii) Tapering (Weeks 9-10). During the titration period, patients will undergo titration of vaporized medication from 4 puffs to 18 puffs, or oral medication from 5 mg qd to 10 mg tid per day. Subjects will be dropped from the study by the end of Week 4 if they are unable to tolerate the minimum amounts of medication described above, and replaced by another volunteer. During the treatment period, subjects will be expected to consume the amount of study medication that they titrated themselves up to by the end of week 4. During the tapering period, patients will slowly withdraw from medication over two weeks. During treatment at home (weeks 1-8), patients will maintain a paper daily diary to record their intake of study medications, and breakthrough pain medications, as well as pain relief measurements. Outcome measure (such as self-report forms and neuropsychological testing) will be collected during the six study visits. If participating in Driving Simulation, subjects with driver licenses will be scheduled for two experimental visits.

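### Two THC tests after randomisation can be turned positive by study drug with no masking of results: the oral-fluid exclusion rule cannot be applied blind, and the week-8 urine screen may separate the THC arms from placebo

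*Protocol*

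**What the plan says.** Both documents claim blinding. Protocol Section 7 speaks of "performing a randomized, double-blind placebo controlled 8-week trial", and SAP Section 1 of a "prospective, randomized, placebo controlled, double blind, phase 2/3 clinical trial". Neither says which staff are blinded.

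**Oral-fluid test.** Protocol Section 9 (Study Visits, just before Outcome Measures) orders a Draeger 5000 oral-fluid THC test for participants who are not in the driving simulation or the microbiome substudy. The reason given is: "This will be done to exclude participants who use their own cannabis seeking pain relief because they were given placebo". No visit, reader, cut-off or masking rule is attached. The 5 ng/ml cut-off earlier in Section 9 is for abstinence at study entry.

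**Urine test.** Protocol Section 9, ARM #2, says that at the start of driving appointments "participants will be given a urine toxicology and a breathalyzer test to test for any illicit substances that is not prescribed by a physician". For participants positive for an illicit substance, "they will either be asked to reschedule or be discontinued from the study", at the principal investigator's discretion. One driving appointment precedes treatment; the other is "a second visit after finishing their 8th week treatment". The panel is not listed there. The only panel defined is the eligibility screen in Section 10: "A urine drug test that screens for 5 categories of drugs: marijuana" is the first category named. Its only THC exception is a prescription; study drug is not mentioned.

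**Analysis.** SAP Section 4.1 makes vaporized cannabis (A) versus dronabinol (B) the primary comparison, A versus placebo (C) secondary and B versus C exploratory. SAP Section 4.1.1 specifies an intent-to-treat analysis. Blinding is assessed by asking participants only, after weeks 1 and 8.

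**The concern.** Two of the three arms take THC for eight weeks, so a THC test during or after treatment reflects the assigned arm as well as conduct.

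The oral-fluid rule therefore has no workable blinded form. A positive means use of own cannabis only if the participant is known to be on placebo. If the reader knows the allocation, the blind is broken for that participant. If not, the rule catches active-arm participants who are taking study drug as directed. Either way, exclusion after randomisation depends on arm, which conflicts with the intent-to-treat analysis.

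The urine screen raises a narrower question. If the panel shows THC, the investigator can learn THC versus placebo before that day's cold-pressor, pain, psychoactive and driving assessments. The knowledge would also precede later adverse-event judgements and the withdrawal-scale calls. If THC counts as illicit, the reschedule-or-discontinue wording could also fall on people for taking study drug. Because blinding is checked in participants only, unblinding of staff would go undetected.

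**Working it through.** **1. The plan's own counts** (SAP Section 5.1: 40 per arm, 16% dropout, 87% of completers licensed).
- Completers per arm: 40 × (1 − 0.16) = 33.6, taken as 33; total 3 × 33 = 99.
- Drivers per arm: 33 × 0.87 = 28.71, taken as 29; total 3 × 29 = 87.

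These match the plan.

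**2. Expected week-8 urine results, if THC is on the panel** (assuming full adherence, a perfect test and no own cannabis use).
- Positive: 2 × 29 = 58 of 87 (67%), all in arms A and B.
- Negative: 29 of 87, all in arm C.

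If THC from study drug counted as illicit, up to 58 of 87 would fall under the reschedule-or-discontinue wording, none of them on placebo.

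**3. What the result tells a reader.**
- Chance of naming the arm without the result: 1/3.
- With it, a negative identifies C and a positive leaves A and B at 50:50: (1/3 × 1) + (2/3 × 1/2) = 2/3.
- Within A and B, the chance stays at 1/2.

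**4. If the test is imperfect.** The documents give no accuracy figures, so these are assumptions. With sensitivity Se and specificity Sp,

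P(placebo | negative) = (1/3 × Sp) / [(1/3 × Sp) + (2/3 × (1 − Se))].

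| Se (Sp = 98%) | P(placebo given negative) |
|---|---|
| 80% | 0.71 |
| 90% | 0.83 |
| 95% | 0.91 |
| 99% | 0.98 |

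All are well above 0.33. Own cannabis use on placebo would make a positive less informative.

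**5. The oral-fluid rule, case by case.** This needs no accuracy figure.

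| Participant | Positive test reflects | Rule applied without allocation | Rule applied with allocation |
|---|---|---|---|
| Placebo | Own cannabis | Excluded, as intended | Excluded, but blind broken |
| Active arm, study drug only | Study drug | Excluded for taking study drug | Kept, but blind broken |
| Active arm, also own cannabis | Both, not separable | Excluded | Own use not detectable |

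No column both preserves the blind and does what the rule intends.

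**6. Size of the oral-fluid group.** It is not stated. The plan implies 99 − 87 = 12 completers without a licence. Licensed people who decline driving add to the group, and microbiome participation may reduce it.

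No sample-size figure changes.

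**The case against.** The strongest reply is that much of the urine half is inferred. The driving section lists no panel and targets illicit substances not prescribed by a physician; study drug supplied under an IND is not obviously one. Neither document says who reads a result, and the appendices are not visible. This stands, so the urine half is conditional on THC being on the panel. The result does, however, feed a decision by the principal investigator at the appointment. Treating study drug as prescribed would remove the action, not the sight of the result.

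A second reply is that someone outside the site, such as the pharmacy, could hold the allocation and apply the oral-fluid rule. That would work, but the protocol does not say so, and exclusion would still depend on arm.

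A third is that driving-day ratings are completed by participants on paper, the driving and tablet measures are instrument-scored, and the cold-pressor test follows a script. This reduces the scope for bias but leaves staff interaction, adverse-event relatedness and discontinuation decisions.

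A reader might also infer four stronger things, which the documents do not support:

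- *The tests reveal the exact arm, including A versus B.* Both arms contain THC. Whether oral and vaporized THC differ in oral fluid is not in the documents.
- *The primary pain data are biased.* The post-treatment urine test comes after week 8, when the diary entries have been made. (The title of Table 3 also mentions 2 weeks, but the ARM #2 text, Protocol Section 20 and SAP Section 1 give two driving visits in all, one of them before treatment.) The visit for the oral-fluid test is not stated.
- *The week-8 blinding questions are asked after the blind is broken.* Nothing orders them after the urine test or says participants learn the result.
- *The six-week statement in Protocol Section 14 proves urine positivity.* It concerns "hair or blood for a minimum of six weeks after vaporizing", not urine or oral fluid.

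**Conclusion.** The concern holds within limits.

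The oral-fluid rule is the firm part. As written, it either requires the allocation or excludes active-arm participants for taking study drug, and arm-dependent exclusion conflicts with the intent-to-treat analysis. This rests only on the stated purpose and on two of three arms receiving THC.

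The urine screen is a conditional part. If its panel matches the eligibility panel, the week-8 result separates THC arms from placebo, with 58 expected positive and 29 expected negative of 87 under full adherence and a perfect test. The separation is weaker if either assumption fails.

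The comparisons exposed are A versus C and B versus C, on staff-run secondary outcomes (SAP Sections 4.2.2 to 4.2.4) and safety (SAP Section 3.1). The primary A versus B comparison is not shown to be affected, nor is diary pain already recorded. The placebo comparisons still matter because Aim 1 asks whether either treatment reduces pain more than placebo, and Aims 2 and 3 also compare with placebo.

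**What to change.** 1. **Oral fluid (Protocol Section 9).** State the visit. Send THC results obtained after randomisation only to the investigational pharmacy or laboratory, and withhold them from site staff and participants until database lock. Use them only in a post-lock sensitivity analysis. Once the allocation is known, a positive in the placebo arm can be interpreted; in an active arm it still cannot separate own THC from study THC.
2. **Analysis (SAP Section 4.1.1).** State that a THC result removes no randomised participant from the intent-to-treat analysis, and define the sensitivity analysis.
3. **Urine (Protocol Section 9, ARM #2).** List the panel, and use one without a visible THC result at the week-8 driving visit. The Hour 1 blood THC sample in Table 3, drawn before that day's dose, already covers drivers; its results should be withheld in the same way.
4. **Reconciliation.** The oral-fluid text, the driving-visit text and the Section 10 panel must agree on whether the illicit-substance and exclusion wording covers THC from study drug, and must name who sees each result. What should lead to discontinuation is for the sponsor and investigators to decide; this review does not choose that rule.

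The cost is protocol and SAP wording and a different urine panel, with no extra visits or staff. The downside is that suspected use of own cannabis is not acted on in real time.
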